4.4 Statistical Methods

4.4.1 General analyses principles

We will calculate and compare all effectiveness outcomes for the two trial arms using prespecified analyses following the intention-to-treat principle. Statistical analysis methods to determine intervention effect on outcomes will be used that are appropriate for CRTs with a small number of clusters. Analysis of cluster-level summaries is based on a total of 20 clusters (10 per arm), each comprised of one health center, and each being given equal weight. Effect estimates will be reported with 95% confidence intervals, and an associated P-value.

4.4.2 Baseline data

Baseline variables will be cross-tabulated to check for appropriate balance between study arms and to characterize the study population using summary statistics both at cluster and individual levels (**Table 1, 2**).

Cluster (*i.e.* health center) level data will be collapsed across study arms and compared using mean, median and range with standard deviations and/or interquartile ranges as appropriate. The basis of this analysis will be data on demographics, health center and laboratory infrastructure, organizational hierarchy, Xpert referral network, and TB testing and treatment collected during site assessment, recruitment, and guidelines training.

Individual level data for all patients eligible for analysis will also be collapsed across study arms and compared using mean, median and range with standard deviations and/or interquartile ranges as appropriate. These individual factors include age, sex, HIV status, and ART status.

We will also summarize data obtained during the pre-randomization period for the cohort of health centers and patients who are being enrolled in the study and randomized to a trial arm.

Descriptive data between control and intervention arms will be presented in tabular format in lieu of formal statistical comparison or significance tests, and will be reviewed to confirm comparability and identify any substantial imbalances. Adjusted effect estimates will be calculated by study arm to account for imbalance

of covariates which are risk factors for the outcome of interest. Losses in degrees of freedom due to cluster-level covariate adjustments will be accounted for in all calculations.

4.4.3 Primary analysis of primary outcome

Analysis will be conducted at the cluster (clinic)-level. The outcome is the count of the number treated for microbiologically-confirmed TB within two weeks of referral for sputum-based testing at the clinic-level. Initially Poisson regression will be used, with an offset at the clinic level of the total number of months the clinic contributes individuals to the study (starting from 22 October 2018). Evidence for over-dispersion will be assessed and if over-dispersion is detected then negative binomial regression will be used, using the same offset. Either model will adjust for randomisation strata and the count of microbiologically-confirmed TB cases that initiated on treatment within 14 days in the 12 month period before 22 October 2018. The exact functional form of this covariate will be identified through fractional polynomials or by using \log_e transformation. Further adjustment for clinic-level factors that show imbalance will be explored, though the number of adjustment factors will be limited as all are at the clinic-level. See tables 4 and 5a.

Xpert Ultra cartridges will be used in our intervention (see Outcomes Definitions Section 3.4). Two sensitivity analyses will be performed reclassifying 1) all trace-positive results as negative and 2) trace-positive results in HIV negative patients as true positive (even if not confirmed by a second positive test) to determine the impact of Ultra on the primary outcome.

No sub-group analyses for strata defined at the individual-level (eg., sex and HIV status) will be conducted as the primary outcome analyses is conducted at the cluster-level.

4.4.4 Analysis of secondary outcomes

Secondary outcomes are reported as either counts, proportions, or time to event, and are derived from data collected across routine data sources.

All analyses will adjust for randomisation strata. Intervention effect estimates will be reported for analyses (1) adjusting for randomisation strata only and (2) adjusting for randomisation strata and individual-level (proportions and time to event only) and clinic-level factors considered imbalanced, as outlined below. See table 5b.

4.4.4.1 Count outcomes:

The analytic approach will be the same as described for the primary outcome. . The outcome is the count of the respective outcome at the clinic-level. Analysis will be conducted at the cluster (clinic)-level. Either Poisson or negative binomial regression will be used, depending on over-dispersion. Adjustment will be made for the clinic-level count of the outcome using data in the 12 month period before 22 October 2018. The exact functional form of this covariate will be identified through fractional polynomials or by using \log_e transformation.

4.4.4.2 Proportions

The analysis will give each cluster equal weight. The overall risk for each cluster will be calculated and shown, by strata and arm. A log transformation (where necessary) will be applied to the risk for each cluster. If a cluster has no events, 0.5 event will be added to all clusters in order that the log transformation can be conducted. The mean and standard deviation of these log risks will be used to obtain the geometric mean (GM) and associated 95% CI for each arm of the study.

The risk ratio is estimated using linear regression of the log risks/rates/means on stratum and arm. An approximate standard error for the difference in log (GM) between arms is obtained based on the residual mean square from a two-way analysis of variance (ANOVA) of the cluster log risk on stratum, study arm and the interaction between stratum and study arm. The 95% CI is calculated from this standard error, using a t-statistic with 16 degrees of freedom.

Logistic regression will be used to adjust for any baseline imbalance at the individual level, adopting a two-stage approach. The regression model will include terms for the adjustment factors (individual level) and strata, but not study arm. For each cluster the fitted model will be used to obtain the ratio of observed to expected (O/E) events, and a log transformation will be applied to this ratio, where appropriate.

Linear regression of the log (O/E) on stratum and arm (2-way ANOVA) will be used to estimate the risk ratio. The variance for the ratio of mean O/E is calculated from the residual mean square from an ANOVA of log(O/E) on stratum, arm and the interaction between stratum and arm. The 95% CI is calculated from this variance, using a t-statistic with 16 degrees of freedom. Limited adjustment for individual level factors is only possible; age, sex, HIV status, and ART status. Adjustment will only be done if data completeness for the variable is more than 80% in both trial arms.

If imbalance is observed for the equivalent cluster-level outcome in the 12 month period before 22 October 2018, adjustment at the second stage described above will be conducted, with appropriate adjustment for the degrees of freedom for the intervention effect. The exact functional form of this cluster-level covariate will be identified through fractional polynomials or by using \log_e transformation.

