Health centers will be grouped into two strata using baseline data for the primary outcome (see Outcomes below), and randomized within strata to help reduce between-cluster variation and improve balance between arms at baseline.²⁶ Restriction, a common approach in cluster-randomized trials with a small number of clusters, may be used to help achieve baseline balance of important site- and patient-level covariates.²⁷ We will consider restricting on factors likely to be associated with the primary outcome including health center region (four quadrants of Uganda), health center size (based on volume of patients tested for TB), HIV prevalence among TB patients, and patient cost and satisfaction with care. The restriction factor will be calculated and the validity of the restriction assessed using the validity matrix.²⁸ The Trial Statistician (KF) will be responsible for the randomization. Randomization will be unveiled to health center directors (or their designated representative) at a meeting chaired by the Uganda NTLP Director.

Procedures

The following procedures will occur at site visits to each participating health center. Site visits will occur approximately every 2-4 months throughout the study.

Health center training

Training will occur at the first site visit after health center enrollment and after health center randomization.

Following enrollment, we will conduct TB guideline and registry training at the first pre-randomization site visit. Project staff, an NTLP/NTRL representative and the District TB Officer will conduct the training jointly using a standardized slide set that emphasizes Uganda NTLP guidelines/algorithms for TB diagnosis and treatment. In addition, project staff will assess the completeness of data recording in TB registers, and provide training as needed to improve completeness. Last, project staff will visit all GeneXpert testing hubs that receive samples from project sites, and provide refresher training on GeneXpert device maintenance and operation.

Following randomization, we will conduct a 2-day site visit to each intervention and control health center.

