4.1 Sequence Generation

A random allocation sequence will be generated by STATA 14 (StataCorp LP, College Station, TX). Randomisation of clusters to the intervention or control arm was conducted using stratification and restriction. Stratified randomisation was used to help reduce between-cluster variability and achieve balance at baseline. Using data from 2017 on the percentage of adult clinic attendees being investigated for TB who started TB treatment within 14 days, the clusters were stratified into two equal-sized groups – “low” and “high” percentages of this outcome based on the median. Restricted randomisation was used to help ensure balance for key factors. Variables we restricted on were; year cluster enrolled in project (2017 vs. 2018); sputum transport frequency to Xpert hub; distance to Xpert hub; number of patients evaluated for

TB; percentage starting TB treatment within 14d; urban vs. rural health clinics; HIV prevalence; number of facilities per district. For these restriction criteria the overall proportion of unacceptable allocations was calculated and the validity assessed using the validity matrix.¹ From a total of 63,504 possible randomisations based on two equal-sized strata, applying the restriction criteria resulted in 11,392 randomisations; one of these was chosen at random.

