4.1 Sequence Generation

A random allocation sequence will be generated by STATA 14 (StataCorp LP, College Station, TX). Randomisation of clusters to the intervention or control arm was conducted using stratification and restriction. Stratified randomisation was used to help reduce between-cluster variability and achieve balance at baseline. Using data from 2017 on the percentage of adult clinic attendees being investigated for TB who started TB treatment within 14 days, the clusters were stratified into two equal-sized groups – “low” and “high” percentages of this outcome based on the median. Restricted randomisation was used to help ensure balance for key factors. Variables we restricted on were; year cluster enrolled in project (2017 vs. 2018); sputum transport frequency to Xpert hub; distance to Xpert hub; number of patients evaluated for TB; percentage starting TB treatment within 14 days; urban vs. rural health clinics; HIV prevalence; number of facilities per district. For these restriction criteria the overall proportion of unacceptable allocations was calculated and the the validity assessed using the validity matrix.⁹ From a total of 63,504 possible randomisations based on two equal-sized strata, applying the restriction criteria resulted in 11,392 randomisations; one of these was chosen at random.

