4.4.4.2 Proportions

The analysis will give each cluster equal weight. The overall risk for each cluster will be calculated and shown, by strata and arm. A log transformation (where necessary) will be applied to the risk for each cluster. If a cluster has no events, 0.5 event will be added to all clusters in order that the log transformation can be conducted. The mean and standard deviation of these log risks will be used to obtain the geometric mean (GM) and associated 95% CI for each arm of the study. The risk ratio is estimated using linear regression of the log risks on stratum and arm. An approximate standard error for the difference in log (GM) between arms is obtained based on the residual mean square from a two-way analysis of variance (ANOVA) of the cluster log risk on stratum, study arm and the interaction between stratum and study arm. The 95% CI is calculated from this standard error, using a t-statistic with 16 degrees of freedom. This will be the primary analysis.

Limited adjustment for individual level factors is possible; age, sex, HIV status, and ART status. Adjustment, using a complete case analysis, will only be done if data completeness for the variable is more than 80% in both trial arms and imbalance is observed (not assessed through a P-value). Logistic regression will be used to adjust for any baseline imbalance at the individual level, adopting a two-stage approach. The regression model will include terms for the adjustment factors (individual level) and strata, but not study arm. For each cluster the fitted model will be used to obtain the ratio of observed to expected (O/E) events, and a log transformation will be applied to this ratio, where appropriate.

Linear regression of the log (O/E) on stratum and arm (2-way ANOVA) will be used to estimate the risk ratio. The variance for the ratio of mean O/E is calculated from the residual mean square from an ANOVA of log(O/E) on stratum, arm and the interaction between stratum and arm. The 95% CI is calculated from this variance, using a t-statistic with 16 degrees of freedom

If imbalance is observed for the equivalent cluster-level outcome in the 12 month period before 22 October 2018, adjustment at the second stage described above will be conducted, with appropriate adjustment for the degrees of freedom for the intervention effect. The exact functional form of this cluster-level covariate will be identified through fractional polynomials.

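### The analyses of secondary proportions and times ignore the restricted randomisation, so they are conservative to the extent that the restriction variables predict the outcome; a randomisation test over the 11,392 allowed allocations would correct this at little cost.

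*Combined protocol and SAP*

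**What the plan says.** **Allocation (SAP 4.1).** The clinics were split at the median of the 2017 percentage treated within 14 days: "the clusters were stratified into two equal-sized groups". Restriction followed on eight variables. Three open the SAP's list: "Variables we restricted on were; year cluster enrolled in project (2017 vs. 2018); sputum transport frequency to Xpert hub; distance to Xpert hub". The fourth is the volume of TB evaluations at the clinic. The last four are given as "percentage starting TB treatment within 14 days; urban vs. rural health clinics; HIV prevalence; number of facilities per district". The plan counts 63,504 arrangements under stratification alone and says of those that remained: "applying the restriction criteria resulted in 11,392 randomisations; one of these was chosen at random". The limits themselves are not given.

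**Proportions (SAP 4.4.4.2).** The log risk of each clinic is regressed on stratum and arm. The standard error comes from the residual mean square of an ANOVA on stratum, arm and their interaction. The interval then follows: "The 95% CI is calculated from this standard error, using a t-statistic with 16 degrees of freedom". The amended SAP fixes the status of this analysis: "using a t-statistic with 16 degrees of freedom. This will be the primary analysis".

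**Times (the time-to-event section after 4.4.4.2).** An ANOVA of clinic means or geometric means is used, and the amended SAP also calls it primary. Under 4.4.4 all secondary analyses adjust for the randomisation strata.

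**Adjustment.** For both types, a second analysis may add age, sex, HIV status and ART status, or the clinic's own baseline value of the outcome, when imbalance is seen. No restriction variable is named for adjustment as such, and no randomisation test is planned. Count outcomes differ: their model always includes the clinic's baseline count.

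**The concern.** Restricted randomisation lowers the true variance of the arm difference by ruling out allocations that are unbalanced on the chosen variables. An analysis on stratum and arm does not see this. Its residual mean square still holds all the within-stratum variation those variables explain, so the standard error describes an unrestricted stratified draw.

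The adjustment rule would not normally repair this. It is triggered by observed imbalance, and restriction is meant to prevent imbalance on these variables.

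Some predictive strength is plausible for some outcomes. SAP 3.4 justifies the 14-day window by saying that control-arm diagnosis may take 7 to 10 days depending on how often samples are transported, and transport frequency is one of the eight variables. With only 20 clinics, part of the precision that the design was built to gain may be lost for day-14 proportions and time to diagnosis.

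**Working it through.** **1. The plan's own figures.** Two strata of 10 clinics, five to each arm: C(10,5)² = 252² = 63,504, as stated. The share kept is 11,392 / 63,504 = 17.9%. Degrees of freedom: 20 clinics − 4 stratum-by-arm cells = 16, as stated.

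**2. Effect of the restriction on the variance.** Let R² be the share of within-stratum, between-clinic variance in the outcome that the eight variables explain. Suppose *b* of the eight limits bind and acceptance is 17.9%. For a Mahalanobis-type rule the variance of a restricted covariate's mean difference is multiplied by

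v = P(χ²₍b+2₎ < a) / P(χ²₍b₎ < a), where P(χ²₍b₎ < a) = 0.179.

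This gives v = 0.017, 0.096, 0.174 and 0.40 for b = 1, 2, 3 and 8. If prediction is spread evenly over the eight variables, the variance of the arm difference relative to what the t analysis assumes is

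q = 1 − (1 − v) × R² × b/8.

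**3. Effect on the test.** The two-sided 5% critical value of t on 16 df is 2.120, so the actual size is about P(|t₁₆| > 2.120/√q). Example with b = 8 and R² = 0.4: q = 1 − 0.60 × 0.4 = 0.76, √q = 0.872, 2.120/0.872 = 2.43, size 2.7%.

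Type I error by formula, with simulation results in brackets:

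| Limits that bind | R² = 0.2 | R² = 0.4 | R² = 0.6 |
|---|---|---|---|
| One | 4.8% (4.8%) | 4.5% (4.5%) | 4.3% (4.2%) |
| Two | 4.5% | 4.1% | 3.7% |
| Three | 4.4% | 3.8% | 3.2% |
| Two or three (simulation) | (4.5–4.6%) | (3.9–4.2%) | (3.4–3.6%) |
| All eight | 3.8% (3.6–4.1%) | 2.7% (2.6–2.9%) | 1.8% (1.4–1.9%) |

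The simulations enumerated all 63,504 allocations and kept 11,392 by balance on simulated clinic covariates. They applied the SAP's ANOVA with t on 16 df to data with no effect. With unrestricted stratified allocation the same test gave 4.9 to 5.1%. At R² = 0 the restricted design gave the same.

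The even spread is an assumption. In the extreme case of one binding limit on a variable that carried all of the R², v = 0.017 would apply to the whole R² and the formula gives 3.1% at R² = 0.2.

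**4. Interval width and power.** With all eight limits tight, the t interval is wider than the design needs by about 4 to 7% at R² = 0.2 and 15 to 17% at R² = 0.5. In that setting a randomisation test raised power from 80% to 82%, 85% and 87% at R² = 0.2, 0.4 and 0.6. With one binding limit the excess width, 1/√q − 1, is only about 1% at R² = 0.2 (q = 0.975).

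**5. Ceiling on R².** Sampling error in a clinic's risk cannot be predicted by clinic variables. With k = 0.36 and 268 patients per clinic (SAP 3.5), the cap is about k² / [k² + (1 − p)/(268p)], with k² = 0.1296. At p = 6.7% the sampling term is 0.933/17.96 = 0.052 and the cap is 0.1296/0.1816 = 0.71. Assuming the same k, the cap is 0.52 at p = 3% and 0.26 at p = 1%. Rare outcomes such as RIF resistance can lose little.

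**6. Size of the proposed test.** 5% of 11,392 is 569.6, so at most 569 allocations fall in the rejection region: 569 / 11,392 = 4.995%, whatever R² is and wherever the limits lie. The smallest two-sided P-value is about 2 / 11,392 = 0.0002.

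**The case against.** **The size of the effect is unknown.** This stands. The documents give no R² and no limits. A reader might infer that the error rate falls well below 5%. That needs a high R², tight limits on all eight variables, or a binding limit on one dominant predictor, and the documents establish none of these.

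**The protocol does not say that these eight variables predict these outcomes.** This stands. Its Randomization section says "We will consider restricting on factors likely to be associated with the primary outcome", but of a different candidate list: region, size, HIV prevalence, and patient cost and satisfaction. Only clinic size and HIV prevalence carry over to the final eight, and the statement concerns the primary outcome. SAP 4.1 speaks only of balance on key factors.

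**Tight balance is doubtful.** Number evaluated and percentage treated within 14 days were both restricted, yet the pre-intervention geometric mean number treated was 14.70 in control and 6.49 in intervention clinics (SAP 3.5), a ratio of 14.70/6.49 = 2.27. The data periods may differ, but this counts against assuming that most of the variation was removed.

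**Part is already handled.** The strata use baseline 14-day treatment, one of the eight variables, which lowers the within-stratum R². Adjustment for the clinic's baseline outcome can recover more, but only if imbalance triggers it.

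**The planned analysis is acceptable for 20 clusters.** Agreed. The promise in SAP 4.4.1 of methods suited to few clusters is not broken. None of these objections shows that the restriction is accounted for, and the remedy does not depend on knowing R².

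**Conclusion.** The point holds for secondary proportions and times. Their primary analyses ignore the restriction and are conservative to the extent that the eight variables predict the outcome within strata. Type I error is about 5% if they predict nothing, about 3.6 to 4.8% at R² = 0.2, and roughly 2 to 4% at R² = 0.4 to 0.6. These ranges assume 17.9% acceptance, between one and eight binding limits and, where few limits bind, prediction spread evenly over the eight variables.

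The consequence is lost precision and power on secondary outcomes, not bias or excess false positives. A reader might extend the point to all secondary intervals and P-values, or to the primary outcome. The documents do not support that: count outcomes and the primary outcome use regression that always adjusts for the clinic's baseline count, and they are outside this conclusion.

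**What to change.** In SAP 4.4.4.2 and the time-to-event section:

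- Keep the point estimate from the regression or ANOVA on stratum and arm.
- Take the P-value from the randomisation distribution of that estimate over the 11,392 acceptable allocations.
- Obtain the 95% CI by inverting that test on the log scale, or on whichever scale is analysed. This assumes a constant effect across clinics on that scale.
- Report the t-based interval (16 df for proportions) alongside.

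This is preferable to putting all eight variables in the model, which would leave 16 − 8 = 8 df and raise the critical value from 2.12 to 2.31.

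The cost is a few lines of code and some extra reporting. The acceptable allocations were already enumerated to make the draw, and at R² = 0 essentially nothing is lost. Stating the restriction limits in SAP 4.1 would also let readers judge how tight the balance was.
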